Based on the previously published conceptual framework of PREPARE,²⁷ we also hypothesize 1615 that PREPARE efficacy may vary across several moderator or mediator variables (e.g., health 1616 1617 literacy using the validated Short form Test of Functional Health Literacy in Adults s-TOFHLA, 1618 scores $0-36^{77}$ and dichotomized to limited = 0-22 & adequate = 23-36; clinician-patient language 1619 concordance (concordant versus discordant); and patient's desired role in decision making with 1620 the medical provider using the validated Decision Control Preferences Scale(wants to make 1621 their own decision versus wants doctors/family to make decisions for them).⁷⁸ We also 1622 hypothesize that PREPARE efficacy may be affected by several confounding variables (e.g., self-rated health, "How would you rate your health?" [5-point Likert]^{79,80} dichotomized as fair-to-1623 1624 poor and good-to-excellent and past experiences with ACP including prior documentation of legal forms and documented discussions. We will also assess a full range of patient-reported 1625 characteristics, as these factors may impact patient-clinician communication,^{20,81} such as age 1626 ("What is your date of birth?"), self-reported gender ("What gender do you consider yourself to 1627 1628 be? male, female transgender, other"), finances (able to make ends meet versus not make ends 1629 meet), having a potential surrogate decision maker or not, education ("What is the highest 1630 educational level you have completed?" less than or equal to high school or greater than high 1631 school), internet access in the home (yes or no), and religiosity and spirituality (i.e., "How 1632 religious/spiritual do you consider yourself to be?" on 5-point Likert scale from not-at-all to 1633 extremely).

1634

1635

- 1636
- 1637

Outcome Measures Table

Construct	Measure	# items	English Reliability/Validity	Spanish Reliability/Validity	Baseline	1 week	3 months	6 months	12 months	15 months
	Primary Outcome									
New ACP Documentation	Chart review: ACP documentation (i.e., legal forms and documented goals of care discussions) ^{35,36}				X					X
	Secondary Outcomes									
The Full ACP Process	ACP Engagement Survey: ²⁷ Behavior Change Process Measures (knowledge, contemplation, self-efficacy, readiness)	57	Behavior Change Measures: Cronbach's α = 0.94 (0.91-0.96), ICC= 0.70 (0.54-0.82) ²⁷	-	x	x	x	x	x	

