1649 Our primary analyses will compare change in ACP documentation between study arms from 1650 baseline to 15 months. Secondary outcomes will include ACP Engagement with respect to 5 1651 ACP Actions (yes/no and a 0-25-point scale) and behavior change scores (average 5-point 1652 Likert scores) from baseline to 1 week, and 3, 6, and 12 months. Variables will be assessed for distributional and outlier values using standard summary statistics. Baseline comparability will 1653 1654 be assessed between groups using unpaired t-tests, Chi-square tests or Fisher's exact tests. 1655 Using t-tests or Chi-squared tests, we will also compare patient's age and self-reported gender 1656 between those who refused versus those who enrolled and differences between arms of those 1657 who withdrew versus those who did not. We will use intention-to-treat analysis using SAS 1658 version 9.4 (SAS Institute Inc.) and STATA 15.0 (College Station, TX). All p-values will be 2-1659 tailed and set at .05 for the primary outcome and Bonferroni adjusted for secondary patient-1660 reported outcomes. In addition, because of differences in ACP engagement among English and Spanish speakers,⁸ and based on preferences of our stakeholders and granting agencies, we 1661 1662 decided, a priori, to analyze our results overall and stratified by English and Spanish language. 1663 To compare outcomes between the two arms longitudinally, we will use mixed effects linear, 1664 Poisson, or negative binomial regression for continuous measures and mixed effects logistic regression for dichotomous measures. The mixed effects models will include fixed effects for the 1665 1666 primary modeling terms of time (baseline and 15 months for ACP documentation and baseline 1667 and 1 week, 3 months, 6 months, and 12 months for ACP Engagement with time modeled using 1668 dummy variables to allow for non-linearity); arm (AD-only versus PREPARE); an interaction 1669 term of study arm and time; and a random effect for subjects. We will adjust for the randomization blocking factors limited vs. adequate literacy,⁹⁸ and any predictor variables that 1670 1671 differ between arms. All models also will also be adjusted for baseline ACP documentation and will include random physician intercepts to account for nesting of patients within physicians. We 1672 1673 will use standardized, clinically meaningful effect sizes (i.e., 0.20-0.49 small, 0.50-0.79 medium,

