1700 from longitudinal analyses with repeated measures will be stronger, but to be conservative, we consider power for a single post-intervention time point (e.g., 15 months). A recent meta-1701 1702 analysis of written advance directive documentation studies demonstrated a pooled effect size of 0.50 (95% CI; 0.17 -0.83),¹⁰⁰ as did an RCT of an ACP workbook that included both behavior 1703 change constructs and a social work visit,¹⁰¹ and our prior RCT of an easy-to-read AD at ZSFG 1704 which showed an increased AD completion rate from 7% to 15%.⁸ Because both the 1705 1706 intervention and control arm will receive the easy-to-read advance directive, we assume that 1707 both arms will have an advance directive completion rate of $\leq 15\%$. Based on prior studies, we 1708 assume PREPARE will result in additional benefit of advance directive completion with a 1709 minimum effect size of 0.5 (two-fold increase) above 15%. A sample of 350, (175 per arm), will 1710 afford us 92% power (2-tailed alpha of 0.05) to detect a difference of advance directive 1711 completion rates of 15% in controls vs. 30% in the PREPARE arm and 80% power to detect a difference of 15% vs. 27%. Power is also expected to be strong for the ACP behavioral change 1712 scale outcomes (preliminary data demonstrated a pre-to-post improvement of 0.5 SD).²⁷ With a 1713 1714 conservative assumption that controls will improve by 0.1 to 0.2 SD, we will have 85% to 98% 1715 power, respectively, to conclude that the improvement is better in the PREPARE arm. We 1716 expect a 15% drop out rate at 12 months based on our prior randomized, controlled trial at ZSFG,⁸ and will therefore attempt to recruit 402 patients, or 201 in each arm for each language 1717 1718 (English and Spanish) for a total recruitment of 804 patients.

1719

Our sample size will also allow adequate power to detect clinically important interactions based on potential moderators (literacy, control preferences, language concordance) for our outcomes. In a prior trial of an easy-to-read advance directive in the same patient population with only 200 patients, we found significant interactions for literacy.⁸ Thus, if we consider the power scenario of the control group ACP documentation rate of 15% and the PREPARE group of 28%, and suppose the control group rate is the same (15%) for both levels of the moderating factor, then

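### The planned model for the patient-reported scores tests a difference in change; adjusting for the baseline score already collected would cut its variance by (1 − ρ)/2, where ρ is not given

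*Combined protocol and SAP*

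**What the plan says.** The final protocol's Statistical Analysis Plan describes one mixed-model form for all longitudinal outcomes. Its fixed effects start with the "primary modeling terms of time (baseline and 15 months for ACP documentation and baseline" plus 1 week, 3, 6 and 12 months for ACP Engagement. Baseline is thus a response row. The remaining terms are "dummy variables to allow for non-linearity); arm (AD-only versus PREPARE); an interaction" "term of study arm and time; and a random effect for subjects. We will adjust for the" blocking factor, health literacy, and for any predictors that differ between arms. A random clinician intercept is added.

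The only baseline ACP covariate is a chart variable: "All models also will also be adjusted for baseline ACP documentation". That is not the baseline value of the score being analysed. No sentence sets the arms equal at baseline, and none names the visit at which arm by time is to be tested.

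The Outcome Measures Table schedules the Behavior Change and Action scores, the PHQ-8 and the GAD-7 at baseline and at all four follow-ups. Under Intervention and Comparison Conditions, the website is viewed after the baseline interview, so the baseline score precedes exposure. The SAP gives no separate model for PHQ-8 or GAD-7; I take the same form to apply.

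**The concern.** With baseline as a response and an unconstrained arm effect, the model spends information on estimating an arm difference at a time when randomization makes the expected difference zero. The treatment contrast then carries the full baseline noise of both arms. Adjusting for the baseline score targets the same arm difference at follow-up and removes only the part of the baseline that predicts it, so in large samples it is never less precise.

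At stake is the precision of the main patient-reported secondary outcome and of the two safety scores. It matters most in the language-stratified analyses, which have half the pooled sample and are tested at a Bonferroni-adjusted alpha.

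**Working it through.** **Inputs.** From Sample Size and Power Calculations: 175 analysed and 201 recruited per arm per language; PREPARE improves 0.5 SD and controls 0.1 to 0.2 SD, so the arm difference is 0.4 to 0.3 SD; two-sided alpha 0.05 ("afford us 92% power (2-tailed alpha of 0.05) to detect a difference of advance directive" completion); 15% dropout. From the Outcome Measures Table: Behavior Change "ICC= 0.70 (0.54-0.82"), Action ICC 0.87 (0.79-0.92), GAD-7 ICC 0.83 (English) and 0.64 (Spanish). Preliminary Studies gives 7 days as the retest interval for the engagement survey. No baseline-to-follow-up correlation appears anywhere, so ρ is an assumption, shown over a range.

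**The plan's own figure.** The stated power for the Behavior Change scale is 85% to 98%. With SD 1:
- 201 per arm: 85.3% for 0.3 SD and 98.0% for 0.4 SD. Both reproduce.
- 175 per arm: 80.1% and 96.3%.
- 175 per arm with change-score variance 2(1 − ρ) at ρ = 0.56: 84.9% and 97.9%. Both reproduce.

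The documents do not say which route was used.

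**Variance at one visit** (linear model, complete data, equal SDs, units of SD², clinician clustering left out):
- Planned contrast, a difference in change: 2(1 − ρ).
- Adjusted for the baseline score: 1 − ρ².
- Proportional cut: 1 − (1 − ρ²)/[2(1 − ρ)] = 1 − (1 + ρ)/2 = (1 − ρ)/2.

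In this setting, covariates that are constant over time and enter only as main effects (literacy, chart documentation) leave arm by time unchanged. A generalized least squares check of the random-intercept model with five occasions gave the same variance for the planned contrast. Holding the arms equal at baseline gave the same cuts.

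**Power** for 0.3 SD, 175 per arm: Φ(0.3/√(2v/175) − 1.96). At ρ = 0.5, v = 1 gives Φ(2.806 − 1.96) = 0.80, and v = 0.75 gives Φ(3.240 − 1.96) = 0.90.

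| Assumed ρ | Planned v | Adjusted v | Cut | Planned power | Adjusted power |
|---|---|---|---|---|---|
| 0.2 | 1.60 | 0.96 | 40% | 60% | 82% |
| 0.3 | 1.40 | 0.91 | 35% | 66% | 84% |
| 0.5 | 1.00 | 0.75 | 25% | 80% | 90% |
| 0.7 | 0.60 | 0.51 | 15% | 95% | 98% |

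**The documents' ICCs used as ρ.** Behavior Change: (1 − 0.70)/2 = 15%, or 9% to 23% over its interval. Action: (1 − 0.87)/2 = 6.5%, or 4% to 10.5%. GAD-7: 8.5% (English) and 18% (Spanish). Correlations over 3 to 12 months are probably lower than a 7-day ICC, which would make the gain larger, but that is a judgement.

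**Sensitivity.**
- Monotone dropout reaching 15% by 12 months (assumed pattern): the 12-month cut is 36%, 22%, 13% and 6% at ρ = 0.2, 0.5, 0.7 and 0.87.
- Pooled sample, 350 per arm, ρ = 0.5: 98% against more than 99%.
- Difference of 0.4 SD, 175 per arm, ρ = 0.5: 96% against 99%.
- Alpha 0.025 (assumed; the SAP gives no number for the secondary outcomes), 0.3 SD, 175 per arm, ρ = 0.5: 71% against 84%.
- Unequal SDs as in the pilot (33 before, 22 after), ρ = 0.5: 33² + 22² − 2(0.5)(33)(22) = 847 against 22²(1 − 0.25) = 363, a 57% cut. The pilot had one group of 43 people scored 0-124, so this is only illustrative.

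**The case against.** The planned model is a standard and valid repeated-measures analysis. It uses everyone with any score, and the primary outcome is not involved. In the pooled sample, or for a 0.4 SD difference, power is already high at moderate ρ. The variance identity is exact only for linear models, whereas the SAP also allows "Poisson, or negative binomial regression for continuous measures and mixed effects logistic" regression for dichotomous ones. All of this stands, and it limits the weight of the point without reversing its direction in the linear models.

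Two stronger readings are tempting, and the documents do not support them.

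- A reader might infer that the power section is wrong to say that power "from longitudinal analyses with repeated measures will be stronger, but to be conservative, we consider power for a single post-intervention time point". That sentence introduces the advance directive outcome and gives 15 months as its example; the scores stop at 12 months. It also speaks of repeated measures. A change-score test falls below a post-only test under ρ = 0.5 only if a single visit is tested, and the SAP names none. For the mean of four follow-ups minus baseline, the variance is (1 + 3ρ)/4 + 1 − 2ρ = 1.25(1 − ρ), which is below 1 once ρ exceeds 0.2.
- A reader might infer that a chance baseline imbalance passes whole into the change contrast. With equal SDs, a baseline difference d is expected to carry over to follow-up as ρd, so the change contrast is off by (1 − ρ)d in magnitude.

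There is also a fair objection to one possible remedy. Randomization Procedures places randomization before the baseline interview is scheduled, with sessions of about 2 hours (AD-only) and 3 hours (PREPARE). Repeated no-shows at baseline make a person ineligible. The trial overview instead places randomization after consent. If losses before baseline differ by arm, a model that forces equal baseline means rests on an assumption. Conditioning on the baseline score is less exposed to this.

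**Conclusion.** The point holds as a matter of precision. The SAP leaves the arm difference at baseline free and makes no use of the baseline score as a covariate. In the linear models, baseline adjustment would reduce the single-visit variance by (1 − ρ)/2.

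The size depends on a correlation that the documents do not give. A range of 15% to 40% corresponds exactly to assumed ρ from 0.7 down to 0.2 and should not be read as a property of this trial; the Action scale's own ICC would put the gain at 6.5%. The practical gain is largest within one language stratum, for the smaller (0.3 SD) difference, and at low to moderate ρ.

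The result assumes linear models, equal SDs and large samples, and leaves out clustering. It shows no bias and no invalid test, and it concerns secondary and safety scores only.

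**What to change.** In the Statistical Analysis Plan, give the Behavior Change, Action, PHQ-8 and GAD-7 scores their own model statement. The responses are the follow-up visits only (1 week, 3, 6 and 12 months). The fixed effects are arm, visit, arm by visit, baseline score and baseline score by visit, with the existing adjustments and random effects kept. Name the visit contrast that is tested.

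The cost is wording: the data and software are those already planned. The one small loss is that people with a baseline but no follow-up score leave the model; report their number by arm. A model with a common baseline mean, which keeps them, can serve as a sensitivity analysis. It should state that it assumes no arm-related loss between randomization and the baseline interview, and the two accounts of when randomization occurs should be reconciled so that this can be judged.

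When power for these scores is next stated, give the assumed ρ, the analysed number per arm and the Bonferroni alpha.

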who reported making serious medical decisions. We used semi-structured interviews to ask about what best prepared them for decision making. Qualitative analysis identified 5 overarching themes, beyond ADs, that prepared patients and surrogates for decision making: (1) choose surrogates wisely and verify they know their role, (2) identify goals based on past experiences and personal values, (3) decide whether to grant leeway in surrogate decision making, (4) inform other family and friends of one's wishes to prevent conflict, and (5) ask clinicians guestions. These themes have been incorporated as educational domains of PREPARE.

1124 Validity and reliability of the survey to measure ACP engagement: Surveys were designed 1125 with input from Co-Is and extensive cognitive interviews to measure discrete ACP actions (i.e., 1126 main outcomes: ACP discussions, AD completion,) and ACP behavior change (e.g., 1127 contemplation, self-efficacy, readiness). We recruited 50 older adults, aged \geq 60 years with \geq 2 1128 illnesses (32% female, 42% non-White). Internal consistency 7-day test-retest reliability, and 1129 discriminant validity (scores compared to healthy young adults - 50% female, 75% non-White) 1130 was high. Scores did not differ by race/ethnicity or literacy, p>.05. We will also use validated surveys on ACP attitudes and methods to classify patients into behavior change categories.^{33,34} 1131

Preliminary evidence that PREPARE is beneficial. In a recent pilot,²⁷ we recruited 43 diverse, older adults from low-income senior centers. All subjects rated PREPARE easy to use (mean 9/10-point scale). Pre to post ACP behavior change scores from our validated surveys (0-124 points) increased from 72 ± 33 SD to 87 ± 22, a 15-point increase and an effect size of 0.5.

1136 Vulnerable populations have unique needs. The aforementioned pilot demonstrated that, 1137 unlike our work with Veterans, patients in safety-net settings are less trustful of research and 1138 require in-person recruitment. In addition, these patients are often socially isolated and require 1139 tailored ACP for persons without surrogates or families. They also lack ready access to health 1140 information and ancillary support such as social workers or nurses necessitating access to ACP

outside of the clinical environment. These findings add further evidence for the need to tailor
 PREPARE for vulnerable populations and to test PREPARE within safety-net settings.

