	Action Measures: values identification and discussions	25	Action Measures: ICC*= 0.87 (0.79-0.92) ²⁷							
Implementation: Acceptability	Acceptability and Usability (a) Ease of Use and Understanding (b) Usefulness in decisions & discussions (c) Attitudes about norms or expectations	8 6 6	1 factor explained 81-85% of variance/scale. Kuder- Richardson >0.75 ⁸	1 factor explained 81- 85% of variance/scale. Kuder-Richardson >0.75 ⁸	x					
	Adverse Event Outcomes									
Depression	Patient Health Questionnaire- 8	8	Scores ≥10 100% sensitive and 95% specific for major depressive disorder. ^{73,74}	Scores ≥10 77% sensitive and 100% specific for major	x	x	x	x	x	
Construct	Measure	# items	English Reliability/Validity	Spanish Reliability/Validity	Baseline	1 week	3 months	6 months	12 months	15 months
------------------------------------	--	---------	--	---	----------	--------	----------	----------	-----------	-----------
				depressive disorder ⁸²						
Anxiety	GAD-7 ⁷⁵	7	Cronbach's α = 0.92 ⁷⁵ ICC*= 0.83	Cronbach's $\alpha = 0.88^{76}$ ICC*= 0.64	х	х	х	х	х	
	Exploratory Outcome									
Percent increase in ACP activities	N (%) participants who increased their Behavior Change or Action scores from baseline (i.e., estimated slope > 0)		-	-	x	x	x	x	x	
	Demographic Information									
Demographic Information	Age, gender, race/ethnicity ⁸³ , marital status, and education				x					
Finances	"In general, how do your finances usually work out at the end of the month?"	1	Associated with functional impairment and co-morbidity ⁸⁴	-	x					
Socioeconomic Social Standing	Social standing ladder (i.e. place an "x" where you think you stand relative to other people in society)	1	Associated with functional decline ⁸⁵	-	x					
	Other Measures									
Health Literacy	Short form Test of Functional Health Literacy in Adults s- TOFHLA, scores 0-36) ⁷⁷ Continuous & dichotomized to limited = 0-22 & adequate	36	Cronbach's α = .97 Correlation coefficient w/ other literacy tests > 0.80 ⁷⁷	Cronbach's α >.95 ⁸⁶	x					

Construct	Measure	# items	English Reliability/Validity	Spanish Reliability/Validity	Baseline	1 week	3 months	6 months	12 months	15 months
	= 23-36									
Patient-clinician language concordance	To clinicians: "How well do you speak Spanish? ⁸⁷ Fluent, very well (concordant) vs. well, fair, or poor"	1	AUROC [†] 94% (CI: 90- 98%) ⁸⁷	AUROC [†] 94% (CI: 90- 98%) ⁸⁷	х					

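### The five-visit engagement model names one subject random effect and no residual covariance, so the 12-month contrast could be anti-conservative (about 7–14% at nominal 5% under assumed but plausible patterns)

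*Combined protocol and SAP*

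**What the plan says.** The Statistical Analysis Plan of the final protocol lists the fixed effects of the longitudinal models as time, arm and arm-by-time. For the engagement scores, time is baseline "and 1 week, 3 months, 6 months, and 12 months for ACP Engagement with time modeled using" dummy variables. The random part is the phrase that closes the list: the interaction "term of study arm and time; and a random effect for subjects". All models also "will include random physician intercepts to account for nesting of patients within physicians". No random slope, residual covariance structure or robust variance is named.

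The significance level is "tailed and set at .05 for the primary outcome and Bonferroni adjusted for secondary" patient-reported outcomes; the SAP does not give the divisor.

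Three other places bear on the covariance:

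- Preliminary Studies reports that pilot behavior change scores "increased from 72 ± 33 SD to 87 ± 22, a 15-point increase and an effect size of 0.5". This was one group of 43 people, all exposed to PREPARE.
- The Outcome Measures Table gives "ICC= 0.70 (0.54-0.82") for the Behavior Change scale and an ICC of "0.87 (0.79-0.92") for the Action scale.
- Preliminary Studies identifies the retest interval: "Internal consistency 7-day test-retest reliability".

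**The concern.** Dummy-coded time frees the means but does nothing for the covariance. With one subject effect and independent residuals, a linear mixed model estimates a single within-person variance and applies it to every change from baseline. If visits differ in variance, or if scores 12 months apart correlate less than scores a week apart, that single value is wrong for individual contrasts. It is too small for some and too large for others.

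The physician intercept does not help, because it cancels from a within-patient change. The engagement scores are the main patient-reported secondary outcome, so the p-values at risk are the ones a reader will look at after the primary result. A Bonferroni step then operates on p-values that are already off.

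**Working it through.** **The plan's own figure.** The documents state power for the behavior change scale (85% to 98%) but no false-positive rate. Power = Φ(d·√(n/2) − 1.96). With n = 201 per arm:

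- d = 0.3: 3.007 − 1.96 = 1.047, giving 85.3%.
- d = 0.4: 4.010 − 1.96 = 2.050, giving 98.0%.

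The figure reproduces. It is a single-time comparison in SD units and contains no between-visit correlation.

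**Inputs from the documents.** Five visits; pilot SDs 33 and 22; 7-day ICCs 0.70 and 0.87; 201 per arm per language; 15% dropout.

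**Assumptions.**

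- Correlation is either constant, or decays exponentially from the 7-day ICC to a chosen 12-month value.
- Where the pilot SDs are used, SD 22 holds at all four follow-ups in both arms. They are applied only to the Behavior Change pattern (ICC 0.70).
- Visit times are nominal. Allowing for baseline falling 1–3 weeks before the clinic visit moves the rates by only a few tenths of a percentage point.

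**Formula (complete data).** Let S be the true 5×5 covariance.

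- The fitted within-person variance is W = [tr(S) − 1′S1/5]/4, that is, mean variance minus mean covariance.
- Model variance of a change: 2W. True variance: S₀₀ + Sⱼⱼ − 2S₀ⱼ.
- With r = true/model, the actual two-sided rate is 2Φ(−z/√r), where z = 1.96 at 0.05 and 2.241 at 0.025.

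**Pilot SDs, constant correlation 0.5.**

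- Mean variance = (1089 + 4×484)/5 = 605.
- Mean covariance = (4×363 + 6×242)/10 = 290.4.
- 2W = 2×314.6 = 629.2. True = 1089 + 484 − 726 = 847.
- r = 1.346, rate 9.1%, for every baseline contrast.

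**Equal SDs (set to 1), 0.70 falling to 0.40.**

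- Mean correlation over the ten pairs is 0.5415, so 2W = 0.917.
- True 12-month variance = 2(1 − 0.40) = 1.20.
- r = 1.309, rate 8.7%. At 1 week r = 0.654, rate 1.5%.

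**Both together, falling to 0.40.** 2W = 577.1; true = 1573 − 0.8×726 = 992.2; r = 1.719; rate 13.5%.

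| Pattern | 12 months, nominal 5% | 12 months, nominal 2.5% | 1 week, nominal 5% | Joint 4-df test, nominal 5% |
|---|---|---|---|---|
| Constant variance and correlation | 5.0% | 2.5% | 5.0% | 5.0% |
| Equal SDs, 0.70 falling to 0.6–0.3 | 6.7–9.1% | 3.6–5.3% | 3.4–1.0% | 5.1–5.8% |
| Pilot SDs, constant 0.3–0.7 | 8.8–9.8% | 5.1–5.8% | 8.8–9.8% | 5.6–6.0% |
| Pilot SDs, 0.70 falling to 0.6–0.3 | 11.5–13.9% | 7.2–9.1% | 7.7–3.5% | 5.9–6.4% |
| Equal SDs, 0.87 falling to 0.8–0.3 (Action) | 7.5–11.6% | 4.2–7.2% | under 3% | 5.3–7.0% |

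The joint rates come from the distribution of the model's Wald statistic under S: a sum of four χ²₁ variables weighted by the eigenvalues of M⁻¹T, where T and M are the true and model covariance matrices of the four changes.

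**Simulation checks of the 12-month contrast.**

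- REML random-intercept fits (201 per arm, 15% dropout, 2000 runs): 5.0% for constant 0.6; 8.1% for 0.70 to 0.50; 9.3% for 0.70 to 0.40; 12.2% for 0.87 to 0.50.
- Separate runs (175 per arm, 4000 runs): about 9.4% with pilot SDs and correlation 0.5; 13.6% with pilot SDs and decay to 0.40.

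**Is the pilot drop in SD chance?** The variance ratio is 1089/484 = 2.25. The Pitman-Morgan statistic is (2.25 − 1)·√41 / (2·√(2.25(1 − ρ²))). It is 2.7 at ρ = 0 and 3.1 at ρ = 0.5 (p about 0.011 and 0.004), if all 43 were measured twice. Chance alone is an unlikely explanation within the pilot.

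**The case against.** A reader might infer that the standard errors are simply wrong and that the 12-month test runs at 9–14% instead of 5%. The documents do not support that.

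- They give no correlation between study visits. A single 7-day ICC is not evidence of decay, and under constant variance and correlation the rate is 5.0%.
- The pilot had one exposed group, no control arm, and a 0–124 scale rather than the 5-point averages analysed here. Carrying SD 22 to 12 months and to the AD-only arm is an extrapolation. Nothing cited shows a variance change for the Action score.
- 5% is not the level the plan uses for these outcomes, since they are Bonferroni adjusted.
- The plan names an arm-by-time interaction but does not single out the 12-month contrast. On a joint test the problem nearly disappears.
- The plan is silent on residual structure and robust errors; it does not rule them out. It says intercepts for physicians but only a random effect for subjects.

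Most of this stands, and it makes the size conditional. It does not remove the point. The plan enumerates its model terms, and the literal reading is a random intercept with independent residuals. Bonferroni adjustment does not repair a misjudged standard error: at 0.025 the assumed patterns still give about 4–9%. Any moderator interactions fitted to these scores would be tested at an unadjusted 0.05 on the same covariance.

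It is also fair that the practical effect may be small. The Veterans trial reported P <.001 for engagement at each follow-up. Variance ratios of 1.34 to 1.76 would move p = .001 to about .004–.013.

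**Conclusion.** The point holds in conditional form. As written, the engagement model imposes equal variance and equal correlation across five visits. The pilot gives some reason to doubt the first, and ordinary expectation gives reason to doubt the second.

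If either fails in the ways examined, the baseline-to-12-month arm contrast has a true rate of about 7–14% at nominal 5%. The upper end needs both failures together. The 1-week contrast errs the other way under decay with equal SDs (about 1–3% from the 0.70 starting value). A joint arm-by-time test stays at about 5–6.5% for the Behavior Change patterns and reaches about 7% for Action only under the steepest decay.

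These are illustrations, not bounds. They rest on assumed correlations, on the pilot SDs carrying over, and on a Bonferroni divisor of 2 where 0.025 is used. Uneven spacing is not itself an error, because time is categorical.

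The primary outcome has two time points and one within-subject correlation, so it is untouched. Coverage of PHQ-8 and GAD-7 is only inferred, because the SAP names no model for them. This is a worthwhile correction to the secondary analyses and does not threaten the trial's main result.

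**What to change.** In the Statistical Analysis Plan, for Behavior Change and Action scores analysed by linear mixed model (and for PHQ-8 and GAD-7 if modelled the same way):

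- specify an unstructured within-subject residual covariance across the five visits, in place of the single subject random effect;
- keep the physician random intercept;
- use Kenward-Roger degrees of freedom;
- if this does not converge, keep the stated random-effect model and use cluster-robust (sandwich) standard errors.

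A Toeplitz structure is not a good fallback, because it indexes correlation by visit order and so treats unevenly spaced visits as equally spaced. The choice among linear, Poisson and negative binomial models is a separate and debatable question, and this change does not require settling it.

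The cost is a sentence or two of SAP text. An unstructured matrix has 5×6/2 = 15 parameters, which about 683 completers (804 × 0.85) support easily, as do about 342 per language (402 × 0.85). The downside is that some standard errors, notably at 12 months, may become larger.

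### The primary model's extra covariates are to be picked by observed imbalance between arms, with no list, threshold or timing, so the exact model cannot be reproduced from the plan

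*Combined protocol and SAP*

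**What the plan says.** All of this is in the Statistical Analysis Plan section of the final protocol (September 2017).

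- The primary comparison: "Our primary analyses will compare change in ACP documentation between study arms from" baseline to 15 months, by mixed effects logistic regression, two-sided at 0.05.
- Fixed terms: the "randomization blocking factors limited vs. adequate literacy", then baseline ACP documentation, and the models "will include random physician intercepts to account for nesting of patients within physicians".
- The open term: after literacy, the adjustment extends to "and any predictor variables that", and the sentence ends "differ between arms. All models also will also be adjusted for baseline ACP documentation and" the physician intercepts.
- The only stated means of finding differences in baseline characteristics between the randomised arms: comparability will "be assessed between groups using unpaired t-tests, Chi-square tests or Fisher's exact tests". No significance level is given for these tests.

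The section lists no candidate variables, defines neither *predictor* nor *differ*, sets no limit on the number added, and does not say when or by whom the choice is made. The same rule stands in the original protocol's analysis section. The summary of SAP changes adds baseline ACP documentation to the models and does not withdraw the rule. No section names a primary model without the add-ons.

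**The concern.** Imbalance is a poor criterion for choosing covariates in a randomised trial. Adjustment helps when a variable predicts the outcome, whether or not it is balanced. A rule driven by imbalance can admit a variable unrelated to ACP documentation and leave out a strong predictor that happens to be even across arms.

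Language is the clearest case. The plan justifies its language-stratified analysis by known differences in ACP engagement between English and Spanish speakers. Yet language is not a blocking factor (Randomization Procedures) and is not a fixed covariate in the pooled model. The recruitment target is 201 per arm within each language, so if that target is met the rule will leave language out.

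The second issue is discretion. Two competent analysts could read the clause differently and fit different primary models. The plan also does not say whether imbalance is judged once or separately within each language. The Data Safety Monitoring Plan makes baseline comparability by arm part of monthly investigator review, and nothing requires the covariates to be settled before outcomes are known.

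**Working it through.** **1. The plan's own power figures.** Inputs from Sample Size and Power Calculations: 175 per arm, two-sided alpha 0.05, 15% vs 30% (stated 92%) and 15% vs 27% (stated 80%). Pooled-variance normal approximation, no continuity correction: power = Φ[(d − 1.96·SE0)/SE1].

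- 15% vs 30%: SE0 = √(2×0.225×0.775/175) = 0.0446; SE1 = √((0.1275+0.21)/175) = 0.0439; (0.15 − 0.0875)/0.0439 = 1.42; power 92.3%.
- 15% vs 27%: SE0 = √(2×0.21×0.79/175) = 0.0435; SE1 = √((0.1275+0.1971)/175) = 0.0431; (0.12 − 0.0853)/0.0431 = 0.80; power 79.0%.

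Both agree with the stated values to within about a point. The calculation contains no covariates, so changing the covariate rule leaves it untouched.

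**2. Size of the candidate pool.** The Outcome Measures Table lists, besides literacy: age, gender, race/ethnicity, marital status, education, finances, social standing, language concordance, desired decision role, internet access, acculturation, functional status, self-rated health, prior ACP experience, social support, possible surrogate, and religion/spirituality. That is 17; baseline PHQ-8 and GAD-7 would make 19. A range of 15 to 20 is reasonable.

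**3. Chance that the rule adds something.** Assume *differ* means p<0.05 and the tests are independent. Neither is stated. P(at least one) = 1 − 0.95^k; expected number = 0.05k.

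| k | P(at least one) | Expected number |
|---|---|---|
| 10 | 40% | 0.50 |
| 15 | 54% | 0.75 |
| 17 | 58% | 0.85 |
| 20 | 64% | 1.00 |

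Several candidates overlap (finances and social standing, for example), and positive correlation lowers these figures.

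**4. What a mechanical rule does to the result.** Illustrative simulation: 700 patients (350 per arm), 14 independent covariates of which 4 are prognostic, 15% control rate at average covariate values, ordinary logistic regression without random effects, covariate added if p<0.05, 4,000 runs per scenario. The alternative is the odds ratio for 15% vs 27%. The fixed model always contains the 4 prognostic covariates.

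| OR per SD of the 4 | Truth | Unadjusted rejects | Selected rejects | Fixed rejects | Verdict differs, selected vs unadjusted |
|---|---|---|---|---|---|
| 1.0 | null | 4.9% | 4.9% | 5.0% | 0.5% |
| 1.35 | null | 4.7% | 4.6% | 5.2% | 0.7% |
| 1.65 | null | 5.0% | 4.6% | 4.5% | 1.1% |
| 1.0 | effect | 97.8% | 97.6% | 97.8% | 0.3% |
| 1.35 | effect | 96.7% | 96.7% | 97.3% | 0.4% |
| 1.65 | effect | 94.3% | 94.8% | 97.1% | 1.5% |

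The Monte Carlo standard error at 5% is √(0.05×0.95/4000) = 0.34 points, so the null rows show no inflation. A covariate was selected in about half of the runs, close to 1 − 0.95^14 = 51%. When one was, the log odds ratio moved by 0.015 to 0.038 on average, at most about 4% on the odds-ratio scale (e^0.038 = 1.04). The visible cost is power: 94.8% against 97.1% when the covariates are strong.

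**The case against.** The strongest reply is that little is at stake. The core of the model is fixed and already contains an obvious predictor, baseline documentation. The moderator models list only literacy, prior documentation and clinician clustering. The clause speaks of predictors, which may mean variables thought to matter for the outcome. The simulation shows no inflation and few changed conclusions.

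Much of this stands, and it rules out several stronger readings that a reader might infer.

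- *The whole covariate set is data-driven.* It is not; only the additions are.
- *Every baseline difference is chance.* Randomization Procedures says that allocation preceded scheduling of the baseline interview, and the eligibility section excludes repeat no-shows to that interview. The visits last about 2 hours in one arm and 3 in the other. Some differences could therefore reflect loss after randomisation. That is a reason to look at the arms side by side, not to let the comparison choose the primary covariates.
- *Outcome data drive the selection.* The documents do not say so. They are silent on timing and blinding.
- *The 54% to 64% measures harm.* It measures only how often a covariate enters.

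The reply does not remove the main point. Even on the narrow reading of *predictor*, imbalance decides which predictors enter. And a simulation of a mechanical rule cannot cover the discretion left by a plan that states no threshold.

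**Conclusion.** The point holds for the additional covariates. Their selection rule is stated but cannot be carried out in only one way, and its criterion is imbalance rather than prognosis. On the assumptions of a 0.05 threshold and 15 to 20 independent tests, an unplanned covariate is more likely than not to enter the primary model.

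The expected damage under a mechanical rule is small: type I error 4.6% to 4.9%, a verdict different from the unadjusted model in 0.3% to 1.5% of simulated trials, and up to about 2 points of power lost when covariates are strong. These figures rest on the simulation's assumptions, including independent covariates and no clustering. The documents do not support a claim that alpha is inflated or the estimate biased by a known amount. The case for change rests on reproducibility, removal of discretion and some precision. It should be made because it is nearly free.

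**What to change.** For the primary model, delete the clause beginning "and any predictor variables that" up to the end of that sentence. State the covariates in full: the literacy stratum as used in blocking (the single question on confidence with forms, which is not the s-TOFHLA used elsewhere in the plan), language in the pooled model, baseline ACP documentation, and the physician random intercept. Any further prognostic variable should be named now, on prior grounds.

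Adjustment for variables found imbalanced can be kept as a labelled sensitivity analysis. Baseline comparisons by arm can stay as a check on loss between randomisation and the baseline interview, with a statement that they do not select primary covariates.

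The cost is a sentence or two of SAP text. No data, patients or visits are added, and the stated power (92% and 80%) and recruitment target (402 per language) are unchanged.
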